Attachment 7. Protocol JVDF Restricted and Prohibited Concomitant Therapy

The table below describes medications, treatments, and drug classes restricted or prohibited, with exceptions and conditions for use during the study treatment period (there are no prohibited therapies during the follow- up period). Patients who, in the assessment by the investigator, require the use of any of the prohibited treatments for clinical management should be removed from the trial. Patients may receive other supportive therapy or vaccinations that the investigator deems to be medically necessary.

Generally, medications or live vaccinations specifically prohibited in the exclusion criteria are not allowed during the ongoing trial.

Therapy	As Needed	Chronic Use	Exceptions or Conditions for Use
Anti-platelet therapy	yes	no	Chronic use of aspirin up to 325 mg/day is permitted.
Anticoagulation therapy	no	Yes, with restrictions	At enrollment, patients on full-dose anticoagulation must be on a stable dose (minimum duration 14 days) of oral anticoagulant or low molecular weight heparin or similar agent. If on warfarin, the patient must have an INR ≤ 3 and no active bleeding or pathological condition present that carries a high risk of bleeding (e.g., tumor involving major vessels or known varices).
Anti-cancer biological therapy	no	no	
Chemotherapy	no	no	
Colony-stimulating factors	yes	no	Follow local guidelines.
Erythroid growth factors	yes	no	Follow local guidelines.
Experimental medicines or investigational agents	no	no	Other than ramucirumab or pembrolizumab
Glucocorticoids	no	no	Systemic glucocorticoids are permitted to modulate symptoms from an event of suspected immunologic etiology. The use of physiologic doses of corticosteroids may be approved after consultation with the Sponsor. Note: Inhaled steroids are allowed for management of asthma.
Immunotherapy (including vaccinations)	no	no	Other than pembrolizumab OR inhaled steroids Live vaccines are NOT allowed within 30 days prior to the first study treatment and while participating in the trial. Examples of live vaccines include, but are not limited to, the following: measles, mumps, rubella, chicken pox, yellow fever, rabies, BCG, and typhoid (oral) vaccine. Seasonal influenza vaccines for injection are generally killed virus vaccines and are allowed. However, intranasal influenza vaccines (e.g., Flu - Mist®) are live attenuated vaccines, and are not allowed.
NSAIDs	yes	no	Chronic use of aspirin up to 325 mg/day is permitted. In addition, in certain medical situations, NSAIDs may be the best treatment option (for example, for pain management). Increased risk of bleeding should be considered by the treating physician and the patient.
Radiation therapy	no	no	Localized radiation therapy to a symptomatic, solitary lesion or to the brain may be allowed after consultation with the Sponsor.

Abbreviations: INR = international normalized ratio; NSAIDs = nonsteroidal anti-inflammatory drugs.

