6.6.1. Ramucirumab Dose Adjustments, Delays, and Discontinuation

The ramucirumab dose may need to be delayed and/or reduced if the patient experiences an adverse event, including an adverse event of special interest (AESI) (Section [8.2.1.1.1](#)). Doses may be delayed to allow time for the patient to recover from the event. Certain AEs require immediate and permanent discontinuation of study treatment. Any patient who requires a dose reduction will continue to receive a reduced dose until discontinuation from ramucirumab or discontinuation from the study. Any patient who has had 2 dose reductions and who experiences a toxicity that would cause a third dose reduction must be discontinued from ramucirumab.

[Table JVDF.3](#) presents the ramucirumab dose reductions for each treatment cohort.

[Table JVDF.4](#) presents the criteria for dose modifications and dose discontinuations applicable if the patient experiences a ramucirumab AESI or other AEs at least possibly related to ramucirumab.

Table JVDF.3.

Ramucirumab Dose Reductions^a

	Dose Schedule 1: Gastric-GEJ/BTC (21-day Cycle)	Dose Schedule 2: Gastric-GEJ/NSCLC/Urothelial (21-day Cycle)
Starting dose	8 mg/kg on D1, D8	10 mg/kg on Day 1
First dose reduction	6 mg/kg on Day 1, Day 8	8 mg/kg on Day 1
Second dose reduction	5 mg/kg on Day 1, Day 8	6 mg/kg on Day 1

Abbreviations: BTC = biliary tract cancer; D = Day; GEJ = gastroesophageal; NSCLC = non-small cell lung cancer.

^a Ramucirumab dose reductions are allowed between cycles and within a given cycle.

Table JVDF.4. Dose-Modification Guidelines for Ramucirumab for Adverse Events at Least Possibly Related to Ramucirumab, including Adverse Events of Special Interest

Adverse Event NOTE: All Specific Adverse Events Listed are defined as AESIs in Section 8.2.1.1.1).		CTCAE Grade	Dose-Modification Guidelines NOTES: Dose reductions to occur as defined in Table JVDF.3. Treating physicians can modify or discontinue ramucirumab more conservatively than in the guidance below.
1.	Infusion-related reaction		
1.a.	Infusion-related reaction	2	
Interrupt and reduce the infusion rate by 50% for the duration of the infusion and for all future infusions.
 
Prior to all future infusions of ramucirumab, premedicate with:
 
 • an intravenous histamine H1 antagonist, such as diphenhydramine hydrochloride • dexamethasone or equivalent • acetaminophen/paracetamol

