6.9.1.2.2. Supportive Care Agents for Ramucirumab- Guidelines

Supportive care measures may include but are not limited to antiemetic agents, opiate and nonopiate analgesic agents, appetite stimulants, and granulocyte and erythroid growth factors. Guidelines regarding the use of specific supportive care agents are presented below.

6.9.1.2.2.1. Antiemetic Agents

Although emesis is not an expected side effect of ramucirumab, the use of antiemetic agents is permitted at the discretion of the investigator. Acceptable antiemetic agents include 5-HT₃ receptor antagonists (for example, ondansetron), dopamine receptor antagonists (for example, metoclopramide), corticosteroids (for example, dexamethasone), and others.

6.9.1.2.2.2. Analgesic Agents

The use of analgesic agents is permitted at the discretion of the investigator. Opiate and nonopiate analgesic agents are permitted (including acetaminophen/paracetamol); however, use of NSAIDs and/or aspirin is restricted ([Attachment 7](#)).

6.9.1.2.2.3. Appetite Stimulants

The use of appetite stimulants is permitted at the discretion of the investigator. Examples include megestrol acetate, dronabinol, and others.

6.9.1.2.2.4. Granulocyte-Colony Stimulating Factors

The as-needed use of G-CSFs is permitted at the discretion of the investigator based on American Society of Clinical Oncology (ASCO) guidelines (Smith et al. 2006) ([Attachment 7](#)).

6.9.1.2.2.5. Erythroid Growth Factors

The as-needed use of erythroid-stimulating factors (for example, erythropoietin) is permitted at the discretion of the investigator based on ASCO guidelines (Rizzo et al. 2008) ([Attachment 7](#)).

6.9.1.2.2.6. Other Supportive Care Agents

The use of benzodiazepines, antidepressants, laxatives, and other agents that may be helpful in controlling disease-related symptoms are also permitted and encouraged, except as prohibited in [Attachment 7](#).

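### Table JVDF.4 calls for dexamethasone premedication after a Grade 2 ramucirumab infusion reaction, but Attachment 7 prohibits glucocorticoids, has no exception that clearly covers it, and attaches a removal rule

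*Protocol*

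**What the plan says.** Table JVDF.4, line 1.a (Protocol 6.6.1) covers a Grade 2 infusion-related reaction to ramucirumab. Besides interrupting and slowing the infusion, it says: "Prior to all future infusions of ramucirumab, premedicate with" three agents, namely an intravenous H1 antagonist, "dexamethasone or equivalent", and acetaminophen/paracetamol. None of the three is marked optional.

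Attachment 7, which Section 6.9 names as the list of restricted and excluded therapies, applies throughout the study treatment period. Its glucocorticoid row is negative in both the as-needed and the chronic-use columns. The row gives three exceptions:

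- "Systemic glucocorticoids are permitted to modulate symptoms from an event of suspected immunologic etiology";
- steroids at physiologic dose levels, if the sponsor is consulted and agrees;
- inhaled steroids for asthma.

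The opening text of Attachment 7 adds that patients who, in the investigator's assessment, "require the use of any of the prohibited treatments for clinical management should be removed from the trial".

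Protocol 6.9.1.2.2.1 leaves antiemetics to the investigator's discretion. It names corticosteroids, with dexamethasone as the example, next to 5-HT3 and dopamine receptor antagonists. It does not refer to Attachment 7.

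**The concern.** One part of the protocol tells the site to give a drug class that another part prohibits, and the second part attaches removal from the trial to needing it. A patient with the same Grade 2 reaction could then be premedicated and continued at one site and removed at another.

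Two trial outputs are directly exposed. The first is disposition and the protocol-violation listing. The second is DLT evaluability in Phase 1a, where a dose schedule may be judged on as few as 3 patients. How the reaction is handled is also a patient-safety matter, so sites should not have to guess which text governs.

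**Working it through.** No figure in the plan is in dispute, so the check is a comparison of the texts, followed by simple arithmetic for scale.

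1. **Does line 1.a call for a glucocorticoid?** Yes. The wording is imperative and applies before every later ramucirumab infusion. The permitted substitute for dexamethasone is an equivalent, which is still a glucocorticoid. The latitude stated at the head of the table, "Treating physicians can modify or discontinue ramucirumab more conservatively than in the guidance below", covers changing or stopping ramucirumab. It does not mention omitting the premedication.

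2. **Does an Attachment 7 exception cover it?**
   - Immunologic exception: it allows steroids to modulate symptoms. Premedication is given before an infusion, when there may be no symptoms to modulate. Protocol 6.6.2 and 6.9.1.3 use the immunologic wording for pembrolizumab events.
   - Physiologic doses: this needs consultation with the sponsor. Line 1.a gives no dose and mentions no consultation.
   - Inhaled steroids: not relevant to this use.

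   Attachment 7 names neither infusion-reaction premedication nor Table JVDF.4.

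3. **Is the removal condition met?** For a patient who continues ramucirumab under line 1.a, the investigator is giving a prohibited class because the protocol's own management calls for it. Read literally, that meets the condition. Sections 7.1 and 7.2 list no steroid-use criterion, so they do not settle the matter. They also separate stopping study treatment from leaving the study, and Attachment 7 does not say which it means by removal.

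4. **Is there a precedence rule?** Neither passage says which one governs.

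5. **Where it would show in the data.**
   - SAP 5.3.2 has violation categories for excluded treatments and for patients who stay on after a withdrawal criterion is met. A patient managed under line 1.a could be listed under both.
   - Protocol 6.1.1.1.1 says reactions during the infusion are not DLTs. Protocol 6.7 makes a patient who leaves the study before the 21-day observation is complete, for a reason other than a DLT, non-evaluable. Schedule 1 has a Day 8 infusion, so the first premedicated infusion can fall inside that window. One such removal would be 1 of as few as 3 evaluable patients and would call for a replacement.

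6. **Scale.**
   - Weight of one patient in a cohort: 1/25 = 4%; 1/15 = 6.7%.
   - Upper bound on premedicated infusions for one patient, assuming the reaction occurs at the first infusion and all 35 cycles are given: Schedule 1, 35 × 2 − 1 = 69; Schedule 2, 35 − 1 = 34.
   - The share of patients with a Grade 2 reaction is not given, so the number affected cannot be computed.

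7. **Antiemetic text.** The neighbouring paragraphs on analgesics, growth factors and other agents all refer to Attachment 7; this one does not. It permits a use that Attachment 7 does not except, without warning the site.

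**The case against.** The strongest defence is that the protocol can be read as consistent.

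- Protocol 8.2.1.1.1 lets infusion symptoms be coded as allergic reaction, anaphylaxis or cytokine release, and anti-drug antibodies are sampled when a reaction occurs. An infusion reaction might therefore count as immunologic.
- Section 6.9 lists premedication separately from concomitant medication, so the specific instruction might prevail over the general row.
- The table is titled as guidelines.
- Section 6.1.1 says the Pharmacy Manuals carry premedication instructions. They are not available here and may be clearer.

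These readings are arguable, but none is stated as the rule. The first fits treatment of a reaction better than prevention of the next one. A site has to choose between the readings, and that is the problem.

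The defence does succeed against three stronger readings that a reader might infer.

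- **That no site can comply with both the antiemetic text and Attachment 7.** It can. The antiemetic text is permissive and offers non-steroid options, so the permission is too broad but it is not a contradictory instruction.
- **That removal is automatic.** Attachment 7 makes it depend on the investigator's assessment and words it as something that should happen.
- **That DCR, PFS and DoR are distorted.** The documents do not show this. SAP 5.2.1.7 keeps every treated patient in the analysis set, and SAP 5.2.1.4 keeps patients without post-baseline assessments in the DCR denominator. The tumor-assessment footnotes in Attachment 1 plan imaging after treatment stops without progression. A possible effect remains. Section 8.1.2 says only that imaging may continue after withdrawal, and a patient removed before any post-baseline scan, with none later, would be a DCR non-responder. If that patient had not died, PFS would be censored at first treatment (SAP Table JVDF.3, rule 2).

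**Conclusion.** The inconsistency between Table JVDF.4 line 1.a and Attachment 7 is real on the current text and should be corrected. It applies to any patient who has a Grade 2 ramucirumab infusion reaction and continues ramucirumab. The likely consequences are inconsistent decisions on continuation, avoidable entries in the violation listing and, in Phase 1a Schedule 1, the possible loss of a DLT-evaluable patient. The antiemetic text is a secondary gap.

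The conclusion rests on reading premedication as outside the immunologic exception, or at least not clearly inside it, and on nothing in the unavailable Pharmacy Manuals settling the question. The number of patients is unknown. The cohort percentages give the weight of one patient and are not an estimate of the effect. Any effect on efficacy endpoints cannot be quantified from the documents.

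**What to change.** Reconcile Table JVDF.4 line 1.a, Section 6.9.1.2.2.1 and the glucocorticoid row of Attachment 7 so that all three state one position on steroid premedication and on steroid antiemetics. Say explicitly whether either use leads to removal and, if so, whether that means stopping study treatment or leaving the study. Add cross-references between the three places, and apply the same position when classifying violations under SAP 5.3.2. Which clinical rule to adopt is for the sponsor's clinical team.

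The cost is protocol wording. Sample size, assessments and analysis methods do not change.

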Attachment 8. Protocol JVDF Abbreviations and Definitions

Term	Definition
ADA	anti-drug antibody
AE	Any untoward medical occurrence in a patient or clinical investigation patient administered a pharmaceutical product and that does not necessarily have a causal relationship with this treatment. An adverse event can therefore be any unfavorable and unintended sign (including an abnormal laboratory finding), symptom, or disease temporally associated with the use of a medicinal (investigational) product, whether or not related to the medicinal (investigational) product.
AESI	adverse event of special interest
ALT	alanine aminotransferase
ANC	absolute neutrophil count
ASCO	American Society of Clinical Oncology
AST	aspartate aminotransferase
audit	A systematic and independent examination of the trial-related activities and documents to determine whether the evaluated trial-related activities were conducted, and the data were recorded, analyzed, and accurately reported according to the protocol, applicable standard operating procedures (SOPs), good clinical practice (GCP), and the applicable regulatory requirement(s).
BCG	bacillus Calmette-Guérin
blinding/masking	A procedure in which one or more parties to the trial are kept unaware of the treatment assignment(s). Unless otherwise specified, blinding will remain in effect until final database lock. A single-blind study is one in which the investigator and/or his staff are aware of the treatment but the patient is not, or vice versa, or when the sponsor is aware of the treatment but the investigator and/his staff and the patient are not. A double-blind study is one in which neither the patient nor any of the investigator or sponsor staff who are involved in the treatment or clinical evaluation of the patients are aware of the treatment received.
C_{ave,ss}	average concentration at steady state
CHF	congestive heart failure
C_{max,ss}	maximum concentration at steady state
C_{min,1}	minimum concentration after first dose administration
C_{min,ss}	minimum concentration at steady state

collection database	A computer database where clinical trial data are entered and validated.
complaint	A complaint is any written, electronic, or oral communication that alleges deficiencies related to the identity, quality, purity, durability, reliability, safety or effectiveness, or performance of a drug or drug delivery system.
compliance	Adherence to all the trial-related requirements, good clinical practice (GCP) requirements, and the applicable regulatory requirements.
continued access period	The period between study completion and end of trial during which patients on study treatment (ramucirumab and/or pembrolizumab) who continue to experience clinical benefit and no undue risks may continue to receive study treatment until one of the criteria for discontinuation is met.
CR	complete response
CRC	colorectal cancer
CrCl	creatinine clearance
CRF/eCRF	case report form/electronic case report form
	Sometimes referred to as clinical report form: A printed or electronic form for recording study participants' data during a clinical study, as required by the protocol.
CRP	clinical research physician
	Individual responsible for the medical conduct of the study. Responsibilities of the CRP may be performed by a physician, clinical research scientist, global safety physician, or other medical officer.
CRS	clinical research scientist
CSFs	colony-stimulating factors
CT	computed tomography
CTCAE	Common Terminology Criteria for Adverse Events
CTLA-4	cytotoxic T-lymphocyte-associated antigen-4
DCR	disease control rate
DKA	diabetic ketoacidosis
DLT	dose-limiting toxicity
DOR	duration of response
ECG	electrocardiogram
ECHO	echocardiogram
ECI	event of clinical interest

ECOG PS	Eastern Cooperative Oncology Group performance status
end of trial	End of trial is after study completion and after the last patient has discontinued study treatment and completed any applicable continued access follow-up.
enroll	The act of assigning a patient to a treatment. Patients who are enrolled in the trial are those who have been assigned to a treatment.
enter	Patients entered into a trial are those who sign the informed consent form directly or through their legally acceptable representatives.
ERB/IRB	ethical review board/institutional review board
	A board or committee (institutional, regional, or national) composed of medical and nonmedical members whose responsibility is to verify that the safety, welfare, and human rights of the patients participating in a clinical trial are protected.
EU	European Union
FOLFIRI	irinotecan, 5-fluorouracil, and folinic acid
FSH	follicle-stimulating hormone
GCP	good clinical practice
G-CSF	granulocyte colony-stimulating factor
GEJ	gastroesophageal junction
GI	gastrointestinal
GM-CSF	granulocyte macrophage colony-stimulating factor
HIV	human immunodeficiency virus
HR	hazard ratio
IB	Investigator's Brochure
ICF	informed consent form
ICH	International Conference on Harmonisation
IK	immunogenicity
Informed consent	A process by which a patient voluntarily confirms his or her willingness to participate in a particular trial, after having been informed of all aspects of the trial that are relevant to the patient's decision to participate. Informed consent is documented by means of a written, signed, and dated informed consent form.
INR	international normalized ratio

interim analysis	An interim analysis is an analysis of clinical trial data, separated into treatment groups, that is conducted before the final reporting database is created/locked.
investigational product (IP)	A pharmaceutical form of an active ingredient substance or placebo being tested, or used as a reference, in a clinical trial. Investigational product (IP) includes a product with a marketing authorization when: 
1. used or assembled (formulated or packaged) in a way different from the authorized form,2. used for an unauthorized indication, or3. used to gain further information about the authorized form.
	In this study, the IPs are ramucirumab and pembrolizumab.
investigator	A person responsible for the conduct of the clinical trial at a trial site. If a trial is conducted by a team of individuals at a trial site, the investigator is the responsible leader of the team and may be called the principal investigator.
IRR	infusion-related reaction
irRECIST	immune-related Response Evaluation Criteria In Solid Tumors
IV	intravenous
legal representative	An individual, judicial, or other body authorized under applicable law to consent on behalf of a prospective patient to the patient's participation in the clinical study.
Lilly Safety System	Global safety database that tracks and reports serious adverse and spontaneous events occurring while using a drug/drug delivery system.
mAb	monoclonal antibody
MedDRA	Medical Dictionary for Regulatory Activities
MMR	mismatch-repair
MRI	magnetic resonance imaging
MTD	maximum tolerated dose
MUGA	multiple-gated acquisition
NCI	National Cancer Institute

non-investigational product (non-IP)	A non-investigational product (non-IP) is a product that is not being tested or used as a reference in the trial but is provided to patients and used in accordance with the protocol. Examples of non-IPs include the following:
	
• Concomitant or rescue/escape medication for preventive, diagnostic, or therapeutic reasons• Concomitant or rescue/escape medication to ensure that adequate medical care is provided for the patient• A product used in accordance with the protocol to induce a physiological response.
NSAID	non-steroidal anti-inflammatory drug
NSCLC	non-small cell lung cancer
ORR	overall response rate
OS	overall survival
patient	A study participant who has the disease or condition for which the investigational product is targeted.
PBMC	peripheral blood mononuclear cells
PD	progressive disease
PD-1	programmed death-1 T-cell co-receptor
PET	positron emission tomography
PFS	progression-free survival
PK	pharmacokinetic(s)
PR	partial response
Q2W	every 2 weeks
Q3W	every 3 weeks
randomize	the process of assigning patients to an experimental group on a random basis
RECIST	Response Evaluation Criteria In Solid Tumors
reporting database	A point-in-time copy of the collection database. The final reporting database is used to produce the analyses and output reports for interim or final analyses of data.
re-screen	to screen a patient who was previously declared a screen failure for the same study
RPLS	reversible posterior leukoencephalopathy syndrome
SAE	serious adverse event

SAP	statistical analysis plan
screen	The act of determining if an individual meets minimum requirements to become part of a pool of potential candidates for participation in a clinical study.
screen failure	patient who does not meet one or more criteria required for participation in a trial
SD	stable disease
SOC	system organ class
Study completion	This study will be considered complete after the final analysis and evaluation of the Phase 1b study endpoints is performed.
SUSAR	suspected unexpected serious adverse reactions
T1DM	type 1 diabetes mellitus
TEAE	treatment-emergent adverse event Any untoward medical occurrence that either occurs or worsens at any time after treatment baseline and that does not necessarily have to have a causal relationship with this treatment.
TSH	thyroid stimulating hormone
TTR	time to first response
ULN	upper limit of normal
US	United States
VEGF	vascular endothelial growth factor
VTE	venous thromboembolic event

**Attachment 9. Protocol JVDF Amendment(b)
Summary An Open-Label, Multicenter, Phase 1 Study of
Ramucirumab plus Pembrolizumab in Patients with Locally
Advanced and Unresectable or Metastatic Gastric or
Gastroesophageal Junction Adenocarcinoma, Non-Small
Cell Lung Cancer, Transitional Cell Carcinoma of the
Urothelium, or Biliary Tract Cancer**

Overview

Protocol I4T-MC-JVDF, An Open-Label, Multicenter, Phase 1 Study of Ramucirumab plus Pembrolizumab in Patients with Locally Advanced and Unresectable or Metastatic Gastric or Gastroesophageal Junction Adenocarcinoma, Non-Small Cell Lung Cancer, or Transitional Cell Carcinoma of the Urothelium, has been amended. The new protocol is indicated by amendment (b) and will be used to conduct the study in place of any preceding version of the protocol.

The overall changes and rationale for the changes made to this protocol are as follows:

- Addition of title, rationale, study design, entry criteria, study procedures and statistical elements for 3 new Phase 1b expansion Cohorts, to include first-line Gastric-GEJ (Schedule 1), first-line NSCLC patients (Schedule 2), and second or third line BTC patients (Schedule 1). At the time of this amendment, Phase 1A Schedule 1 DLT observation is ongoing; Phase 1A Schedule 2 DLT observation has been completed. For first line Gastric/GEJ and first line NSCLC patients, more frequent tumor imaging schedule (every 4 weeks for the first 12 weeks) is required to monitor anti-tumor response to study treatment and initiate alternative treatment as determined by treating investigators.
- Clarifications and refinements, as follows:
 - The final analysis of safety and preliminary efficacy will occur approximately 2 years after the first patient received first study treatment. Separate interim analyses will occur after all patients in each cohort have completed approximately 24 weeks of study treatment or discontinued for any reason. Safety and preliminary efficacy will be analyzed separately for each cohort.
Rationale: This change was implemented to harmonize the interim analysis and final analysis with the intent of the trial design. There is no change to the study treatment duration for each individual patient (35 cycles, approximately 2 years).
 - In Inclusion Criterion [20], clarified that baseline tumor tissue samples must be evaluable, and elaborated on guidance regarding the submission of tumor tissue samples in Section 8.4.2.

- The timing of the required 1-hour observation periods, to occur between ramucirumab and pembrolizumab administration *and* after pembrolizumab administration, for the first 2 cycles. Rationale: this change was implemented to ensure the consistent implementation of the 1-hour observation periods for Schedule 1 and Schedule 2 patients.
- Two additional categories of events are to be reported as SAEs: 1) new cancers (exception: metastases of cancer under study), and 2) any event associated with an overdose of either study drug, as defined in Section 8.2.1.2.
- For pembrolizumab, immune-related adverse events are no longer labeled as Events of Clinical Interest (ECIs). Similarly, references in the protocol to the detailed Site Guidance Document for Events of Clinical Interest were removed. Two (2) categories of ECIs remain: overdose and abnormal liver function tests (as defined in Section 8.2.1.1.3).
- Pembrolizumab dose modification table “Note” was updated to specify that Grade 2 pneumonitis warrants permanent discontinuation of pembrolizumab (see “Note” in table footnote).
- Pembrolizumab supportive care guidelines for Diarrhea/Colitis (Section 6.9.1.3.2) were updated to eliminate any waiting period before beginning treatment for any Grade 2, 3, or 4 event.
- Other typographical, formatting errors or very minor clarifications (key examples below):
 - The Introduction was updated to reflect current regulatory approval status for ramucirumab and pembrolizumab.
 - In Inclusion Criterion [7], to clarify that the screening period is 28 days.
 - Exclusion Criterion [20], to allow seasonal flu vaccines that do not contain live virus.
 - Dose management for ramucirumab in case of Grade 2 toxicity, investigator “may” reduce ramucirumab dose or discontinue ramucirumab. See footnote b in Table JVDF.4.
 - If radiologic imaging verifies initial progressive disease, tumor assessment should be repeated approximately (not “at least”) 4 weeks later to confirm PD.
 - That “whole” blood sample is collected for pharmacogenetic analysis where local regulations and ERBs allow.
 - That the overall response rates presented in the simulations represented by Table JVDF.8 and Table JVDF.9 are provided as a reference for estimation of statistical power rather than as a basis for any decision criteria.
 - A baseline brain scan by CT or MRI was added in the schedule of events (Attachment 1) to be consistent with inclusion criteria for NSCLC and urothelial cancer patients.
